To provide analgesia while reducing the use of opioids and their associated adverse effects, there are multiple distinct approaches to postoperative donor site pain control. Such methods including continuous subcutaneous local anesthetic, subcutaneous anesthetic injections, topical agents, wound dressings, and nonpharmacological strategies.² Based on a review performed by Sinha et al.², few evidenced based recommendations exist despite the significance of donor site pain in this patient population. Within the category of subcutaneous anesthetic injections, the most robust evidence supports the use of lidocaine with 1:500,000 epinephrine based on a randomized control trial conducted by Gacto et al.⁵ Other common agents used include ropivacaine and bupivacaine, but further studies are needed to make true evidence-based recommendations for their use. Additionally, while these traditional formulations may provide effective analgesia at the donor site, the duration of action is relatively short, lasting 12 hours or less.³

Liposomal bupivacaine (Exparel) is a prolonged release formulation that can extend the duration of donor site analgesia. According to Dissanaike et al.³, Exparel has been shown to provide postsurgical analgesia for up to 72 hours and reduce postsurgical opioid requirements when compared with Bupivacaine or placebo in multiple surgical settings. In the setting of STSG donor site pain, however, Exparel use has not been extensively described. We hypothesize that the use of Exparel at STSG donor sites will improve pain control compared to the current standard of care of lidocaine.

2. We hypothesize that use of liposomal bupivacaine (Exparel) will decrease post-operative pain at the donor site compared to the current standard of care, lidocaine, for split thickness skin grafting in patients with burn injuries. We have two specific aims.

- a. To identify whether pain is decreased in patients receiving Exparel injections post-operatively at STSG donor sites compared to patients receiving lidocaine injections as measured by pain scores.
- b. To determine if there is a reduction in post-operative opioid pain medication consumption in STSG patients receiving Exparel injections at the donor site compared to patients receiving lidocaine injections.

B. Background and Significance

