3. N/A

II. Research Plan and Design

- A. Study Objectives:** The objective of this study is to determine if use of liposomal bupivacaine (Exparel) decreases postoperative pain at the donor site compared to lidocaine for split thickness skin grafting in patients with burn injuries. In addition, we aim to identify if use of Exparel at the donor site for split thickness autografting decreases opioid pain medication consumption postoperatively compared to use of lidocaine at the donor site in patients with burn injuries.
- B. Study Type and Design:** This study will be a prospective, randomized controlled trial. Study subjects will be blinded to their randomization to avoid bias. The control group will undergo split thickness autografting using the standard protocol, involving injection of lidocaine with epinephrine at the donor site. The experimental group will undergo injection of liposomal bupivacaine (Exparel) at the time of harvest of the skin graft. Baseline pain levels will be obtained for all subjects using a validated pain assessment scale, the

Visual Analog Pain Scale. Postoperatively, time to first opioid pain medication (excluding immediate postoperative recovery from anesthesia), total opioid consumption on a daily basis, and donor site interval pain scores using a validated pain assessment scale will be obtained. The experimental group will then be compared to the control group to determine if there is a significant difference in pain levels, time to first opioid, and overall opioid consumption between the two groups.

C. Sample size, statistical methods, and power calculation

[figure not shown]
1. Patients will be randomized using a computerized random number generator with 1:1 randomization. Differences between groups will be assessed using Chi square test for categorical variables and Student's t test for two means. Confidence intervals will be calculated to 95% and a p value of less than 0.05 will be considered statistically significant.
2. Only subjects will be blinded to their randomization group. Study subject number will be linked to their randomization group. Blinding may be broken if the subject experiences an adverse reaction to the medication utilized for their group so that they are aware that they cannot receive the medication in the future.

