3. We anticipate a reduction in pain scores by 2 points with SD 2.5 in the experimental group. Power analysis for 80% power yields 25 patients per group. We will aim to enroll a total of 50 patients, 25 in each group.

D. Subject Criteria (See Vulnerable Populations appendix, if applicable):

1. Inclusion criteria: State the criteria for inclusion in the study in a specific and detailed manner.
 - E. Age \geq 18 years, English or Spanish speaking, Burn injury with the following parameters: $\leq 20\%$ TBSA partial thickness, $\leq 5\%$ TBSA deep partial or full thickness, first skin autografting procedure for hospitalization, donor site anterior or lateral thigh
2. Exclusion criteria: State the criteria for excluding potential subjects from the study in a specific and detailed manner.
 - E. Chronic pain syndrome on opioid pain medications at baseline, $>20\%$ TBSA partial thickness burn, $>5\%$ TBSA surgical area of burn injury (deep partial or full thickness injury), pregnant women, age < 18 , not first skin autografting procedure during hospitalization, allergy to lidocaine or other local anesthetics, burns to anterior thighs, inability to give informed consent
3. Withdrawal/Termination criteria: Include the specific circumstances in which the subject's participation will be terminated by the investigator. Include any necessary safety precautions to be applied to those who withdraw (tapering drug doses, evaluative x-ray, etc.)
 - E. Serious adverse reactions to lidocaine or liposomal bupivacaine including cardiac event, arrhythmia, seizure, anaphylaxis, and loss of limb. Subjects who experience these reactions will be medically stabilized and undergo standard work-up based upon symptoms. The subject will be unblinded and the medication administered will be documented in their medical record as an allergy. They will be withdrawn from the study and the adverse reaction will be reported to the IRB within 24 hours.
4. Clarify whether a study subject may participate in another research study while participating in this research study.
 - E. Subjects may participate in additional research studies as long as study protocols do not interfere with one another. For example, subjects may not be enrolled in a study comparing experimental pain management or alternative methods of skin autograft harvest.

E. Specific methods and techniques used throughout the study

1. Laboratory tests: No laboratory specimens will be required for participation in this study.

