 - d. Post-operatively, subjects will recover from anesthesia. Once the subject returns to routine care following completion of recovery from surgery, time to first opioid medication will be recorded. The Visual Analog Pain scale will be used to assess donor site pain at set time intervals. This will occur for three total days. The scale will take approximately one minute to complete and is easily completed by non-English speaking subjects as it is a visual scale. Daily narcotic usage will be obtained from the medical record and will be measured in morphine equivalents. Length of stay will be evaluated from the medical record.
3. Harvesting of the split thickness autograft will be performed in the standard fashion as described above. Treatment of partial and full thickness burns with autografting is the standard of care for many patients with burn injuries. Postoperatively and preoperatively, patients will complete a validated pain assessment scale on a daily basis. Pain is routinely assessed as part of postoperative care and nursing management of patients. As part of the study, a pain scale will be used to specifically ask about pain related to the STSG donor site, whereas the pain scale is typically used to ask about global pain in patient care.
4. Split thickness autografts will be harvested from the anterior and lateral thigh of subjects. Harvested skin may be greater than the size of the recipient burn site. Excess skin will be disposed of. No tissue samples will be collected as part of this study.
5. Timeline:

F. Risk/benefit assessment:

1. Physical risk: Risks include potential adverse reaction to liposomal bupivacaine (Exparel) or lidocaine. Adverse reactions associated with liposomal bupivacaine have been shown to be equal in severity and frequency to those expected with the routine use of lidocaine according to the FDA approval for liposomal bupivacaine. Patients in both groups will be undergoing split thickness skin grafting and will be at risk for common surgical post-operative events, including bleeding, infection, and pain.

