7. N/A
8. N/A

B. Sample / Specimen Collection: N/A

C. Tissue Banking Considerations: N/A

D. Procedures to protect subject confidentiality: Patients will be identified by nursing staff as enrolled in the study to collect the post-operative pain scale assessments. Nursing staff are experienced in maintaining patient confidentiality as this is an expectation with all levels of care they provide. Following the data collection process, the study subjects will be deidentified to maintain their confidentiality.

E. Quality Assurance / Monitoring

1. Data that is collected will be self-reported from patients or collected as objective data from the medical record. No subjective assessments will be done by study team members. There is a chance that study subjects could intentionally falsify their pain scores for secondary gain, for example, to receive more narcotic pain medications. To limit this potential, we will not be including patients in the study who have ongoing opioid use for chronic pain or abuse prior to admission.
2. There are no plans for third party monitoring of this study.

V. Data Analysis and Reporting

- A. Statistical and Data Analysis:** Differences between groups will be assessed using Chi square test for categorical variables and Student's t test for two means. Confidence intervals will be calculated to 95% and a p value of less than 0.05 will be considered statistically significant. Final statistical analysis will be conducted by statistician. Interim analysis is planned for at the half way point of the study (20 patients completed). Interim statistically analysis will be conducted by Co-Investigators.
- B. Outcome:** We expect that the experimental group will have decreased pain scores compared to the control group. We estimate a 2 point difference in pain scores for the STSG donor site and that this difference will occur at 1, 2 and 3 days post-op. We expect that opioid consumption and time to first opioid dose will also be decreased in the study group. Our power analysis calculation based on pain score decrease aims to enroll 40 patients in the study and this is our anticipated study end point.
- C. Study results to participants:** Study subjects may submit a written request to receive study results after completion of the study. If requested, results will be mailed to the study subject after completion of data analysis.

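### Donor-site pain is the implied main outcome, but the plan does not say which day, or which summary of days 1 to 3, decides it

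*Combined protocol and SAP*

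**What the plan says.** No outcome is labelled primary. Pain is aim (a) in I.A.2 ("To identify whether pain is decreased in patients receiving Exparel injections post-operatively at STSG donor sites"), and both sample-size statements rest on it. II.C.3 says "We anticipate a reduction in pain scores by 2 points with SD 2.5 in the experimental group" and arrives at 25 per group; no day is attached to the 2 points. V.B says "Our power analysis calculation based on pain score decrease aims to enroll 40 patients in the study", which is 20 per arm at 1:1.

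The only statement linking the effect to days is in V.B: "this difference will occur at 1, 2 and 3 days post-op".

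V.A (repeating II.C.1) begins "Differences between groups will be assessed using Chi square test for categorical variables" and adds Student's t test for two means, 95% confidence intervals and p<0.05. It gives no deciding day, no average or area under the curve, no repeated-measures model, no any-day or all-days rule, no multiplicity adjustment and no sidedness.

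On measurement, II.E.2.d says "The Visual Analog Pain scale will be used to assess donor site pain at set time intervals", for three days in total, and II.E.3 says "patients will complete a validated pain assessment scale on a daily basis". The Timeline item is blank in the text available.

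II.B looks for a "significant difference in pain levels, time to first opioid, and overall opioid consumption between the two groups" without ranking the three. V.B expects time to first opioid to fall in the experimental group.

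**The concern.** With three daily scores per subject and one generic test, the analyst has to decide what counts as success, and nothing fixes that decision beforehand. II.L.1.d calls for an analysis to see whether the endpoints have been met, but no section says what meeting the pain endpoint means. Only subjects are blinded (II.C.2), and co-investigators run the interim analysis (V.A). People who may know the allocation could therefore see outcome data before a rule exists.

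The possible rules behave differently. An any-day rule inflates the chance of a false claim, and an all-days rule costs power. A trial with mixed day results could be reported as a success or a failure depending on a choice made after the data are seen.

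A smaller problem sits beside this. A subject who takes no opioid has no time to first opioid, so a t test has no value for that subject.

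**Working it through.** **Inputs from the documents.** Difference 2 and SD 2.5 (II.C.3); 80% power (II.C.3); alpha 0.05 (V.A); 25 per arm (II.C.3) or 20 per arm (40 in total, V.B); 1:1 allocation (II.C.1).

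**Assumptions.** Two-sided testing; the same 2 points and SD 2.5 on each of days 1 to 3; equal between-day correlation ρ of 0.3 to 0.8; no missing data.

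**1. The plan's own figure.** n per arm = 2(SD/δ)²(z₀.₉₇₅ + z₀.₈₀)² = 2 × 1.5625 × (1.960 + 0.842)² = 24.5, so 25. This reproduces II.C.3 for one two-sided comparison. One-sided 0.05 gives 19.3, so 20, which would match the 40 in V.B; the documents do not say that this is its origin.

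**2. Power of one comparison by t.** The noncentrality is 2/(2.5√(2/n)). At n = 25 it is 2.83 (df 48), giving 79% power. At n = 20 it is 2.53 (df 38), giving 69%.

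**3. Three daily t tests.** With independent days, the chance of at least one false positive in either direction is 1 − 0.95³ = 14.3%. Correlated days were simulated, 100,000 trials per setting.

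| 25 per arm | ρ 0.3 | ρ 0.5 | ρ 0.7 | ρ 0.8 |
|---|---|---|---|---|
| No effect: any day, either direction | 13.5% | 12.5% | 10.7% | 9.7% |
| No effect: any day, favouring drug | 6.7% | 6.3% | 5.4% | 4.8% |
| 2 points daily: all three days significant | 55.5% | 59.5% | 64.3% | 67.4% |
| 2 points daily: some days but not all | 41.6% | 35.3% | 27.2% | 22.2% |

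The comparator for the drug-favouring row is 2.5%, so the inflation is 4.8/2.5 = 1.9 to 6.7/2.5 = 2.7 times. At 20 per arm, all-days power is 41-55% and mixed results occur in 28-53% of trials.

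**4. One test of the three-day mean.** SD of the mean = 2.5√((1 + 2ρ)/3) = 1.83, 2.04, 2.24 and 2.33 for the four correlations. Power by noncentral t is 97%, 92%, 87% and 85% at 25 per arm, and 92%, 86%, 79% and 75% at 20. Simulated two-sided error is about 5%.

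**5. Dilution of the mean (25 per arm, ρ 0.3 to 0.8).** If the 2 points occur on two days only, the mean difference is 4/3 and power is 51-72%. If they occur on one day only, it is 2/3 and power is 17-24%.

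**The case against.** The strongest reply is that the plan intends one comparison of mean pain: that fits a t test for two means and reproduces 25 per group. This reading is tenable and raises no error or power problem at 25 per arm, but the text does not select it or say which day or average it would use.

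A second reply is that V.B means all three days. It states an expected pattern. Taken as a rule, it would leave power below 80% at either sample size over the range shown.

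A third is that the assessment schedule may be in a figure or section not available here. That may be so, but a schedule is not a decision rule, and V.A, where the rule belongs, is available.

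A fourth is that averaging is a choice with a cost. The background describes analgesia of up to 72 hours, so waning by day 3 is plausible. This stands, and step 5 gives its size. The sponsor's own expectation of an effect on all three days is the case that favours the mean.

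Four stronger readings are tempting, and the documents do not support them:
- That the chance of a false claim of benefit is 10-14%. That figure includes days on which the experimental arm is worse, and the hypothesis is directional. The relevant figure is 5-7% against 2.5%.
- That the sponsor plans to claim any significant day. No section says so.
- That daily opioid use (II.B, II.E.2.d) contradicts the 72-hour total in Appendix III. The one can be summed to give the other.
- That scoring at set intervals contradicts daily scoring. Both can hold.

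The wording of II.A also hints that opioid use ranks below pain, though it is not labelled so.

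**Conclusion.** The point holds as a missing decision rule for the implied main outcome. The plan should settle it before outcome data are examined. It does not show that the trial is underpowered for a single prespecified comparison at 25 per arm.

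The gap itself does not depend on the assumed correlation. The sizes do, and they also rest on two-sided testing and an equal effect on each day. The 20-per-arm figures apply only if the 40 in V.B is the real target; the conflict between 40 and 50 is a separate matter.

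The 5% error for a single summary applies only if the interim look at 20 patients cannot declare success or is alpha-adjusted. If it can declare success at unadjusted 0.05, overall two-sided error for one endpoint is roughly 8-9%. That too is a separate issue.

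**What to change.** In V.A, name one primary analysis: the group difference in donor-site VAS averaged over post-operative days 1 to 3, tested at two-sided 0.05. A repeated-measures mixed model that uses every observed day is one way to do this. State which scheduled scores form each day's value and how missing days are handled. Report single days descriptively.

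Adjust for baseline VAS only if it is confirmed to be a useful covariate. It is taken preoperatively (II.E.2.a), before the donor wound exists, and the text does not say whether it asks about the donor site or overall pain.

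Label opioid consumption and time to first opioid as secondary, so that neither alone confirms the pain hypothesis. Analyse time to first opioid by Kaplan-Meier and log-rank, with opioid-free subjects censored at 72 hours or at last observation if earlier. The reason is that a t test has no value for them, not that log-rank is always more powerful. Reconcile V.B's expectation that this time will fall with the hypothesis of better pain control.

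The cost is SAP wording and slightly more analysis, with no extra subjects or data. In return, an effect confined to one or two days is diluted, and a single-day or opioid-only result can no longer be presented as confirmation.

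### The power analysis is said to give 50 patients in section II.C.3 and 40 in section V.B; at 40, two-sided power is about 69%, not the 80% stated in II.C.3

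*Combined protocol and SAP*

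**What the plan says.** Section II.C.3 gives the assumptions: "We anticipate a reduction in pain scores by 2 points with SD 2.5 in the experimental group". It continues: "Power analysis for 80% power yields 25 patients per group. We will aim to enroll a total of 50 patients", with 25 in each arm.

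Section V.B again expects a 2-point difference in donor-site pain, but then states: "Our power analysis calculation based on pain score decrease aims to enroll 40 patients in the study". It describes this number as the expected end of the study. It gives no new SD, significance level or power.

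Section V.A places the interim analysis half-way through the study and equates that with 20 completed patients.

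Sections II.C.1 and V.A give the same analysis method: "Student's t test for two means", 95% confidence intervals, and "a p value of less than 0.05 will be considered statistically significant". Section II.C.1 sets 1:1 randomisation. No section says whether the test is one- or two-sided, and none gives an allowance for dropout.

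**The concern.** Both totals are attributed to a power analysis on the pain score, with the same assumed difference. A single set of inputs cannot give both 25 and 20 per group. Nor does this look like one mistyped digit: 50 appears both as a total and as 25 per arm, while 40 is backed by the interim count of 20.

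The total decides when enrolment stops. A team following V.B would stop ten patients short of the number on which the 80% power statement rests. A null result would then be more likely and harder to interpret.

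The total also fixes the timing of the interim look. Under V.A the co-investigators carry out that analysis, and under II.C.2 only the subjects are blinded. With two totals on paper, the choice between stopping at 40 and going on to 50 could be made after comparative data have been seen.

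**Working it through.** **Inputs.** Difference 2 points and SD 2.5 (II.C.3), so the standardised effect is 2/2.5 = 0.8. Power 80% (II.C.3). Significance level 0.05, Student's t test and 1:1 allocation (II.C.1). Two-sided testing is an inference, tested below.

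**1. Reproduce the figure in II.C.3.** By the normal approximation,

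n per group = 2 × [(1.960 + 0.8416) × 2.5 / 2]² = 2 × (3.502)² = 24.53, which rounds up to 25.

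This matches II.C.3. Solving with the noncentral t distribution gives 25.52, which rounds up to 26. So 25 per group is the usual normal-approximation answer, at most one patient per arm short by the t test.

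**2. Power at each total, two-sided 0.05.** By the normal approximation, power = Φ(0.8 × √(n/2) − 1.960):

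- n = 20: 0.8 × √10 = 2.530; Φ(0.570) = 71.6%
- n = 25: 0.8 × √12.5 = 2.828; Φ(0.868) = 80.7%

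The t-test figures use the noncentral t distribution with 2n − 2 degrees of freedom and the same noncentrality (2.530 and 2.828).

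| Total | Per group | Power, t test | Power, normal | Chance of missing the effect (t test) |
|---|---|---|---|---|
| 40 | 20 | 69.3% | 71.6% | 30.7% |
| 50 | 25 | 79.1% | 80.7% | 20.9% |
| 52 | 26 | 80.7% | 82.2% | 19.3% |

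**3. What would make 40 correct?** For 80% power by two-sided t test with 20 per group, the standardised effect must be 0.909. That means a difference of 0.909 × 2.5 = 2.27 points with SD 2.5, or an SD of 2/0.909 = 2.20 with a difference of 2 points. The protocol states neither.

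**4. Does a one-sided test reconcile the totals?** At one-sided 0.05:

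| Total | Power, t test | Power, normal |
|---|---|---|
| 40 | 79.9% | 81.2% |
| 50 | 87.4% | 88.2% |

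This would explain 40, but it would contradict the 80% that II.C.3 attaches to 25 per group.

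**5. Interim count.** 20/40 = 50%, whereas 20/50 = 40%. The half-way look in V.A therefore assumes a total of 40.

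**The case against.** The strongest counter-argument is that the plan never says two-sided, and its hypothesis is directional. A one-sided 0.05 test gives almost exactly 80% power with 20 per group, and this may be where 40 came from. That is a fair caution: the 69% figure rests on an inferred two-sided test and should be labelled so. It does not remove the contradiction. Under a one-sided test the figure in II.C.3 would be wrong instead, and the 95% intervals paired with a 0.05 threshold point to two-sided testing.

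A second reading is that 50 are enrolled so that 40 complete, a 20% loss (1 − 40/50). The text does not support it. V.B gives 40 as an enrolment target, II.C.3 takes 25 per group straight from the 80% calculation, and no dropout rate appears.

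Third, V.B attaches no power figure to 40, and neither section is given precedence. Both points stand. The 80% belongs to II.C.3, where it is right by the normal approximation, and the loss of power occurs only if 40 governs. If 50 governs, the fault is outdated text in V.A and V.B. Even then the document holds two incompatible enrolment targets.

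**Conclusion.** The concern holds. The protocol has no single sample size: its power analysis is credited with 50 patients in II.C.3 and 40 in V.B, and the interim count in V.A follows the 40. The inputs given support 50.

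If V.B governs, power is 69.3% by the planned t test (71.6% by normal approximation), about 8 to 11 points below the 80% in II.C.3. These figures assume a true 2-point difference, a common SD of 2.5, two-sided 0.05, equal arms and no loss of patients. The conflict between the totals does not depend on sidedness. This must be corrected, because the number concerned decides when the trial stops.

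**What to change.** Choose one total, use it throughout, and state in II.C.3 that the test is two-sided at 0.05.

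- **If 50 is the target:** change V.B to 50 patients, 25 per group, and move the half-way analysis in V.A to 25 completed patients. Name the method behind the power figure: 80.7% by normal approximation, or about 79% by t test. If 80% by t test is wanted, 26 per group (52 in total) reaches it.
- **If 40 is the target:** change II.C.3 to 20 per group and 40 in total, and remove the 80% claim. State either about 69% power for a 2-point difference, or 80% power for a difference of about 2.3 points. The interim count of 20 can then stay.

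In either case, tie the midpoint review in II.L, which gives no patient number, to the same total.

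On paper this is a wording change. Keeping 50 honours a target the protocol already states, but a site that has been working to 40 would need ten more patients and a later interim look. Keeping 40 requires no more patients, at the price of a less favourable power statement.
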